*Examining disparity driven vergence as a potential
diagnostic test for mild traumatic brain injury (mTBI)*

NCT Number NCT03529799

1) **Protocol Title**

Examining disparity driven vergence as a potential diagnostic test for mild traumatic brain injury (mTBI)

2) **IRB Review History***

None.

3) **Objectives***

Specific Aim 1 (SA1): Determine the validity and safety of disparity driven vergence testing with a portable goggle system using a pseudorandom ternary sequence of frequencies on a group of normal subjects.

Specific Aim 2 (SA2): Determine the vergence testing control values using a portable goggle system using a pseudorandom ternary sequence of frequencies on a group of normal subjects.

Specific Aim 3 (SA3): Determine the vergence testing values with a portable goggle system using a pseudorandom ternary sequence of frequencies on a group of subjects with history of mild traumatic brain injury and compare this to values in normal subjects.

4) **Background**

Vergence eye movements for focusing on objects include either convergence, the coordinated movement of both eyes towards the midline, or divergence, the coordination movement of both eyes towards the periphery. These eye movements are thought to be controlled by complex neurophysiological mechanisms that can be susceptible to damage by traumatic brain injury. Known involved areas in vergence include the oculomotor nucleus, cerebellum, and visual association cortex (Conn 2016), all of which can sustain damage during head trauma.

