feasible, we propose a pseudorandom ternary sequence approach to frequency distribution during disparity driven vergence to allow rapid analysis over a wide range of frequencies. Essentially, a pseudorandom frequency distribution can help extrapolate data to a larger frequency data set. We will also be evaluating the safety and side effect profile of using the goggles using a medical symptom questionnaire.

5) **Inclusion and Exclusion Criteria**

Inclusion:

- Aged 18 or older
- Both females and males

Exclusion:

- Central processing disorder
- Impaired vision without corrective lenses (max 20/60 uncorrected)
- Moderate to severe hearing loss (>55dB PTA, <50% word identification)
- Vestibular disorder except for patients recruited for SA3
- History of ear surgery other than myringotomy with or without tube placement
- Pregnant women
- Prisoners
- Adults unable to consent

6) **Number of Subjects**

60 subjects – 30 normal controls (no mTBI), 30 patients with mTBI.

7) **Recruitment Methods**

Normal subjects will be recruited from a pool of patients from a population who are unaffiliated or affiliated with University of Miami and meet inclusion criteria and not excluded by exclusion criteria. The faculty and students of any University of Miami School will be recruited through advertising in e-mails. Emails will be sent to staff and faculty associated with the UM Clinical Research Building (CRB) that have their emails stored in the UM Outlook server. Subjects will not be paid to participate. Students and staff will be assured that their participation will have no effect on their school performance or grades.

8) mTBI patients will be recruited by convenience from a pool of patients with history of mTBI and no prior vestibular disorders that present to the UM CRB Otology Clinic of [name] (SA3)”. The determination of their fitness for participation will be made during [name] clinical history and physical by asking about the history of the head injury and past medical history.

9) **Study Timelines**

Vestibular tests will take 15 minutes.

10) **Study Endpoints**

Each participant’s study will be completed when they have completed the vergence testing and other vestibular tests. At that point, the data will be de- identified.

11) **Procedures Involved**

The study will be conducted in 2 phases in which each phase comprises of thirty participants.

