In the first phase, thirty participants without mTBI who meet the inclusion criteria and are not excluded will be chosen to participate. Participants will sign an informed consent document and undergo 1 session of vergence testing, along with a series of vestibular tests. After this testing, the data will be de-identified and will only be labeled with sex and age of patient.

In the second phase, thirty participants with mTBI who meet inclusion criteria and are not excluded will be chosen to participate. Participants will sign an informed consent document and undergo 1 session of vergence testing, along with a series of vestibular tests. After this testing the data will be de-identified and will only be labeled with sex and age of patient.

After the session, patients will be given a medical symptom/toxicity questionnaire (MSQ) to evaluate for any side effects.and the SCAT-5 questionnaire, which will evaluate their current symptoms.

For each vestibular test and data to be obtained, see table below:

Test	Activity	Outcome OR Ordinal Value
Vergence Pursuit	Focusing on object moving forward and backwards	0 - 100
Spontaneous Nystagmus	Focusing on an object	Normal / Abnormal (Side)
Saccades ~ Horizontal Random	Focusing on objects randomly in horizontal axis	Normal / Abnormal (Side)
Saccades ~ Vertical Random	Focusing on objects randomly in vertical axis	Normal / Abnormal (Side)
Smooth Pursuit Horizontal ~ 0.1 Hz	Tracking objects in horizontal axis, at 0.1 Hz	Normal / Abnormal (Side)
Smooth Pursuit Horizontal ~0.75 Hz	Tracking objects in horizontal axis, at 0.75 Hz	Normal / Abnormal (Side)
Smooth Pursuit Vertical ~0.1 Hz	Tracking objects in vertical axis, at 0.1 Hz	Normal / Abnormal (Side)

Smooth Pursuit Vertical ~0.75Hz	Tracking objects in vertical axis, at 0.75 Hz	Normal / Abnormal (Side)
Predictive Saccades	Tracking an object moving in predictable manner	Percent (%) Error
Antisaccade	Moving eyes away from visual onset	% Error
OKN (optokinetic nystagmus) Trapezoidal	Tracking moving field	Normal / Abnormal (Side)
Visual Reaction Time	Reaction time to object	Seconds
Saccades and Reaction Time	Reaction time to off-center object	Seconds
Auditory Reaction Time	Reaction time to sound	Seconds
Self-Paced Saccade	Saccadic motion between two fixed targets	0 - 100
Pupil Reflex	Normal light reflex	0 - 100
Subjective Visual Vertical	Ability to perceive subjective tilt	0 - 100

12) **Data Storage**

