The only data to be stored will be the results of the vergence tests and vestibular testing done during the two sessions. These results will be tied together by a subject number that will also link to the sex of the patient and age of the patient. No PHI that identifies any participant will be kept. All the previously described data will be stored on the PI's computer and used for analyses purposes in room 580 of the clinical research building at the University of Miami Medical Center located at [name]. It will be password protected, and unique identifiers used for subject protection. Data will not be distributed, except in the form of peer-reviewed publication or oral presentation maintain the confidentiality of the subjects.

13) **Data Management***

Group mean data and single subject design will be utilized. In the group mean data scoring on each of the sessions will be aggregated for each of the specific aims. First session scores will be compared to second session scores using standard statistical methods with significance defined as $p < 0.05$. For the single subject design the number of subjects for each vestibular tests for each aim who have a significant difference in scores between the first and second session will be calculated and analyzed with descriptive statistics. In this way the investigators can calculate the difference between each test on the two sessions for each protocol, as it is very possible that some tests may be significantly different between the sessions and some tests will not.

Data will be stored on the PI's computer and used for analyses purposes in room 580 of the clinical research building at the University of Miami Medical Center located at [name]. It will be password protected, and unique identifiers used for subject protection. Data will not be distributed, except in the form of peer-reviewed publication or oral presentation maintain the confidentiality of the subjects. . No PHI that can identify any subjects will be kept beyond the second session of testing.

14) **Withdrawal of Subjects**

Subjects can withdraw at any time but if they withdraw their data will not be used and they will be replaced in the study by a new subject.

15) **Risks to Subjects**

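### SA3 needs an mTBI-versus-control comparison, but Section 13 tests only first against second session and gives the stored age and sex no role in any analysis

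*Combined protocol and SAP*

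**What the plan says.** - **Aim.** Section 3 (SA3) asks for vergence values from a pseudorandom ternary sequence in people with a history of mTBI, to "compare this to values in normal subjects". This is a between-group question. Section 6 sets 30 controls and 30 patients.
- **Patients.** Item 8: "mTBI patients will be recruited by convenience from a pool of patients with history of mTBI and no prior vestibular disorders". The setting is one otology clinic.
- **Controls.** Section 7 draws them "from a population who are unaffiliated or affiliated with University of Miami". The only route it describes is e-mail: "The faculty and students of any University of Miami School will be recruited through advertising in e-mails", with messages also going to staff. Section 5 sets a minimum age of 18 and no upper limit. No matching or balancing is described.
- **Sessions.** Under Section 11 each group will "undergo 1 session of vergence testing, along with a series of vestibular tests".
- **Analysis.** Section 13: "First session scores will be compared to second session scores using standard statistical methods", with significance at p < 0.05. It adds a count of subjects whose own scores differ between the two sessions.
- **Data kept.** In Section 11 the de-identified data "will only be labeled with sex and age of patient". In Section 12 results are tied by "a subject number that will also link to the sex of the patient and age of the patient". Neither section lists group membership as a stored label.

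**The concern.** The stated analysis does not fit the design. It needs two sessions per person where there is one, and it contains no mTBI-versus-control test. The SA3 comparison, its outcome and its covariates could therefore be settled after the data have been seen.

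The second issue is what an unplanned comparison would probably look like. A plain two-group test between people recruited by different routes would take up any difference in age or sex mix that is related to vergence. That could produce an apparent mTBI effect or hide a real one. Both variables are already stored, so the plan could deal with this at no data cost, but it does not commit to doing so.

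**Working it through.** **1. Aim, design and test side by side**

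| Item | Section | Content |
|---|---|---|
| Question | 3 (SA3) | mTBI values against normal values |
| Sessions per person | 11 | 1 |
| Inferential test | 13 | first session against second session |
| Per-subject analysis | 13 | count of subjects whose scores differ between sessions |
| Role of age and sex | 13 | none stated |

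With one session there is no second score, so neither Section 13 analysis can be computed. If a second session were added, the test would measure change within people, not the group difference.

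**2. The plan's own figure.** The total of 60 cannot be reproduced, because no effect size, SD or power is given. At 30 per group, two-sided 5% (sidedness assumed), a t-test with 58 df detects 0.736 SD with 80% power.

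**3. Possible size of confounding.** Every input here is an assumption; the documents give neither group's age or sex mix nor any link between these and vergence.

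Spurious difference in SD units: d = r × g, where r is the within-group correlation of age with the score and g is the age gap in within-group SDs. The false-positive rate of the unadjusted t-test comes from the noncentral t, 58 df, noncentrality d × √(30/2) = 3.873 d.

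| r | g | d = r × g | False positives |
|---|---|---|---|
| any | 0 | 0 | 5% |
| 0.2 | 0.5 | 0.1 | 6.7% |
| 0.3 | 1 | 0.3 | 20.8% |
| 0.5 | 1 | 0.5 | 47.8% |

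The bias can also run against a real effect. With a true difference of 0.75 SD, power is 81.5%. An opposing bias of 0.3 SD leaves 0.45 SD and 40.3% power; a bias of 0.5 SD leaves 0.25 SD and 15.9%.

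**4. What adjustment does.** In simulations of 20,000 runs per cell with no true effect, over r of 0 to 0.5 and g of 0 to 1.5, a linear model with group, age and sex held the false-positive rate at about 5%. This assumes that the linear form is right.

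It does not remove referral selection. If a bias of 0.3 SD from that source remains, the adjusted test still gives about 14% to 25% false positives: 0.3/1.28 = 0.23 SD at the least precise end of the age grid, and 0.3/0.88 = 0.34 SD at the most precise.

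**5. What adjustment costs in precision.** Detectable difference = 0.736 × (adjusted SE / unadjusted SE), with simulated SE ratios:

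| Assumed situation | SE ratio | Detectable at 80% power |
|---|---|---|
| r 0.5, equal ages | 0.88 | 0.65 SD |
| r 0.3, equal ages | 0.97 | 0.71 SD |
| r 0.5, gap 1 SD | 0.99 | 0.73 SD |
| r 0.3, gap 1 SD | 1.09 | 0.80 SD |
| r 0.3, gap 1.5 SD | 1.22 | 0.90 SD |
| r 0, gap 1.5 SD | 1.28 | 0.94 SD |
| as above, sex 30% v 70% and unrelated to score | 1.36 | 1.00 SD |

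As a rough check for age alone, the large-sample ratio is √[(1 − r²)(1 + g²/4)]. It gives √0.75 = 0.87 for the first row and √1.5625 = 1.25 for r 0, gap 1.5 SD, close to the simulated 0.88 and 1.28.

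**The case against.** The best defence is that the two sessions in Section 13 mean the two phases of Section 11, so that the groups are in fact compared. Section 13's per-subject count tells against this: it needs both scores from the same person, and nobody is in both phases. Even if the reading is granted, the test is unnamed and age and sex still have no role.

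Several other objections stand in part:

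- **Unspecified methods.** The reference to standard methods does not rule out adjustment. It does not commit to it either.
- **Control source.** Section 7 also calls the controls patients, and Section 26 has participants consented at the ENT clinic. The contrast between sources is therefore less sharp than e-mail against clinic suggests. The described routes still differ.
- **Adjusted analysis as the lead result.** This is partly a choice; matching or balancing on age and sex at recruitment is an alternative. Adjustment can lose precision, as shown above, which is one reason to report both results.
- **Group label.** The phases are separate and codes are kept, so group is probably recoverable. Stating that it is stored is a small clarification.
- **Outcome.** It is tempting to take the Vergence Pursuit score (0 to 100) in the Section 11 table as the SA3 outcome. The documents never equate it with the value from the pseudorandom ternary sequence, so the sponsor has to name the outcome.

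**Conclusion.** The point holds. As written, Section 13 cannot be carried out on one session per person and does not answer SA3. That rests on the text alone and needs no assumption.

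The confounding is a risk of unknown size. The 7% to 48% range follows from assumed spurious differences of 0.1 to 0.5 SD and shows what could happen, not what is likely here. With equal ages and sex mix the rate stays at 5%.

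A reader might infer more in three places:

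- **That the groups do differ in age or sex.** The documents give no such data.
- **That the comparison will be chosen after the data are seen.** The text supports only that it could be.
- **That Section 5 and item 8 contradict each other on vestibular disorder.** Section 5 lifts the exclusion for SA3 patients, and item 8 asks for no prior disorder. The two agree if prior means before the injury, which item 8 does not say. This is a separate ambiguity that does not bear on the age and sex question, and those passages should be reconciled.

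**What to change.** In Section 13, replace the session comparison for SA3 with:

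> For SA3, the vergence value obtained with the pseudorandom ternary sequence [the sponsor to name the single value before analysis] will be compared between mTBI and control participants by a linear model with group, age and sex. The adjusted mTBI-minus-control difference and its 95% CI will be reported, with the unadjusted difference and each group's age and sex distribution alongside. Selection by clinic referral and convenience is not removed by this adjustment and will be reported as a limitation.

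Also state in Sections 11 and 12 that group membership is kept with the subject number.

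A sensitivity analysis that drops participants with Abnormal test results is not advised. Most of those tests measure eye movements, which mTBI may itself affect, so the exclusion could remove a real difference.

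Cost: wording and 2 degrees of freedom, with no new measurement. The difference detectable at 80% power is about 0.74 SD unadjusted and, under the assumed inputs, about 0.65 to 1.00 SD adjusted. It is worst when the groups differ greatly in age or sex and these are unrelated to the score.

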None anticipated since this is not more than minimal risk.

25) **Economic Burden to Subjects**

None anticipated.

26) **Consent Process**

Consent will be obtained by the PI, Sub-I, or study coordinator in the Ear Clinic at the University of Miami Medical Center any participants who wish to enroll in the study will be consented at the ENT clinic prior to initiating any study procedures. Informed consent will be obtained in writing via the attached documents. Participants will be taken into a private room to read the consent form and have any questions regarding the study answered by a research team member.

Waiver or Alteration of Consent Process (consent will not be obtained, required information will not be disclosed, or the research involves deception)

No Waiver being sought

Subjects who are not yet adults (infants, children, teenagers)

Not part of subject population

Cognitively Impaired Adults

Not part of subject population

Adults Unable to Consent

Not included in subject population

References

Conn PM. "Vision." *Conn's Translational Neuroscience*. San Diego: Academic Press, 2017. 399-438.

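### mTBI patients are a convenience sample from one clinic with no rule or log for who is invited, so selection bias in the SA3 comparison cannot be excluded or assessed

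*Combined protocol and SAP*

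**What the plan says.** Section 8 (recruitment of mTBI patients) states the sampling method: "mTBI patients will be recruited by convenience from a pool of patients with history of mTBI and no prior vestibular disorders", taken from those who present to one otology clinic. On eligibility it says "The determination of their fitness for participation will be made during [name] clinical history and physical", and the sentence goes on to give the means: "by asking about the history of the head injury and past medical history".

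Section 5 sets only age and sex as inclusion criteria. No criterion there requires or excludes an eye-movement abnormality. The nearest one is an exclusion: "Vestibular disorder except for patients recruited for SA3".

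Section 7 brings in the controls differently, from people with or without a university affiliation, using e-mail advertising: "Emails will be sent to staff and faculty associated with the UM Clinical Research Building".

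Section 11 places study testing after consent: "Participants will sign an informed consent document and undergo 1 session of vergence testing, along with a series of vestibular tests". Section 26 agrees that participants "will be consented at the ENT clinic prior to initiating any study procedures". Section 12 limits stored data to test results linked to a subject number, sex and age.

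The protocol describes no consecutive-invitation rule, no screening log and no written case definition of mTBI.

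**The concern.** SA3 compares vergence values in mTBI patients with those in normal subjects. That comparison is informative only if the patients enrolled resemble the patients they stand for.

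Two decisions put a patient in the mTBI group. The first is whether the patient is fit, and Section 8 ties this to the history. The second is which fit patients are asked, and the protocol leaves this to convenience. The second decision is taken in a clinic visit where complaints have been heard and a physical examination is under way. Visual or balance complaints, or signs noticed on examination, may be related to vergence performance. If they influence who is asked, the mTBI mean moves for reasons unrelated to mTBI.

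The movement can go either way. Inviting patients who seem more affected would enlarge a difference. Preferring patients who seem able to complete testing, or removing those with vestibular problems under Section 8, could shrink one. With no log, and with only results, age and sex stored, nobody could later tell which of these happened, or whether any did.

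**Working it through.** The protocol gives no effect size, standard deviation or power statement, so there is no figure of its own to reproduce. The calculation below is an illustration on assumed inputs.

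**From the protocol**
- 30 controls and 30 mTBI patients (Section 6).
- Significance at p < 0.05 (Section 13, where it is attached to first versus second session scores).

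**Assumed**
- No true difference between groups; vergence score normal with SD 1.
- Two-sided two-sample t-test (sidedness and test are not stated).
- The clinic forms an impression of each patient that correlates ρ with the vergence score.
- Patients in the worse half on that impression are invited at k times the rate of the others, with k = 1.5, 2 or 3.

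**Shift in the mTBI mean**

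The worse half makes up k/(k+1) of those invited, and the mean distance of each half from the centre is √(2/π) = 0.798 SD. Hence

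shift = ρ × (k − 1)/(k + 1) × 0.798 SD.

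At ρ = 1: 0.2 × 0.798 = 0.16; 0.333 × 0.798 = 0.27; 0.5 × 0.798 = 0.40 SD. At ρ = 0.5 these halve to 0.08, 0.13 and 0.20. At ρ = 0.2 they are 0.03, 0.05 and 0.08.

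**False-positive rate**

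The standard error of the difference is √(2/30) = 0.258 SD. As a hand check for ρ = 0.5, k = 3: 0.199/0.258 = 0.77, so the rejection rate is about P(Z > 1.96 − 0.77) + P(Z < −1.96 − 0.77) = 0.118 + 0.003 = 12%. Simulated t-tests give:

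| Correlation ρ | k = 1.5 | k = 2 | k = 3 |
|---|---|---|---|
| 0 | 5% | 5% | 5% |
| 0.2 | 5.2% | 5.6% | 6.1% |
| 0.5 | 6.1% | 8.0% | 12.1% |
| 1 | 9.4% | 18.3% | 36.1% |

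Repeat runs of 40,000 simulated trials agree to within about half a percentage point.

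The bottom row needs the clinical impression to rank patients exactly as the goggle-measured score does. It is a ceiling for these values of k. Under the null the two-sided rate is the same if patients who appear better are favoured; only the sign of the shift changes.

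**Sections 5 and 8 side by side**

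Section 5 exempts SA3 patients from the vestibular-disorder exclusion. Section 8 draws the same patients from people without prior vestibular disorders. A patient with such a history is admissible under one and not the other, which adds to the discretion at the point of invitation.

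**The case against.** The strongest reply is that Section 8 names its basis, and that basis is the history of the injury and past medical history. No section makes an eye-movement finding a criterion or says that vergence is examined in the clinic physical. The study's vergence test follows consent, so its result is unknown at selection. The measured response is to a pseudorandom ternary sequence delivered by goggles, which a bedside impression may predict poorly. Controls are screened too, under the same Section 5 exclusions, and Section 11 speaks of participants being chosen in both phases. Convenience sampling is also common in small exploratory comparisons.

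Much of this stands. A reader might infer that enrolment depends on eye-movement findings and would manufacture the SA3 difference, or that selection can act in the mTBI group only. The documents support neither. That the person inviting patients would use eye-movement signs is an inference: the text does not provide for it, though it does not rule it out. Nor does the protocol's silence on a log establish that none is kept.

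What the reply does not answer is that the history governs fitness and not the choice among fit patients. Selection also needs only something correlated with the outcome, not the study measurement itself, and complaints heard in the history could serve.

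**Conclusion.** The point holds as a weakness in how cases are sampled. Invitation is discretionary, no consecutive rule or log is described, and controls come by another route, so selection bias in SA3 can be neither excluded nor assessed, in either direction.

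Its size is unknown. It ranges from nothing, if selection is unrelated to vergence, through a modest rise for correlations of 0.2 to 0.5 (at most about 12% for the invitation ratios shown), to 36% at the extreme of perfect correlation and a threefold ratio. A reader might take the 36% as the expected error. It is not, because the documents give neither the correlation nor the invitation ratio. The case for change rests on the low cost of removing the doubt, not on evidence that such selection will occur.

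**What to change.** In Section 8, replace the convenience wording with three statements:
- Consecutive clinic patients who report a history of mTBI are invited.
- Eligibility is decided from the written criteria and the history, before or independently of any eye-movement examination.
- An anonymous log is kept of the numbers eligible, invited, refused and enrolled, with reasons.

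Reconcile the Section 5 exemption for SA3 patients with the Section 8 condition on prior vestibular disorders, so that the written criteria can be read in only one way.

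The cost is a few protocol sentences, a one-page log, a little more clinic effort and possibly slower recruitment. Consecutive invitation does not change the referral spectrum of a single otology clinic, and deciding from the history still means hearing complaints. The first should be stated as a limitation when SA3 is reported. The consecutive rule and the log are what limit the second.

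### SA1 asks about the safety of vergence testing, but the only side-effect form follows vergence and 16 other listed tests, so a reported symptom cannot be attributed to vergence

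*Combined protocol and SAP*

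**What the plan says.** Section 3 (Objectives) sets the SA1 target as "Determine the validity and safety of disparity driven vergence testing with a portable goggle system using a pseudorandom ternary sequence", in normal subjects. The last sentence of Section 4 (Background) words the safety target more broadly: "We will also be evaluating the safety and side effect profile of using the goggles using a medical symptom questionnaire".

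Section 11 (Procedures Involved) has each participant "undergo 1 session of vergence testing, along with a series of vestibular tests". It then states: "After the session, patients will be given a medical symptom/toxicity questionnaire (MSQ) to evaluate for any side effects". The same sentence adds "the SCAT-5 questionnaire, which will evaluate their current symptoms", at the same time point. No form is described before the session or between vergence and the other tests, and there is no rule for attributing a symptom to a test.

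The list of tests is introduced with "For each vestibular test and data to be obtained, see table below". Vergence Pursuit is its first row ("Focusing on object moving forward and backwards"). The table is not described as a running order, and no order is given elsewhere. Section 20 (Resources Available) says that the goggles come programmed in advance with the battery. Section 9 gives 15 minutes for the vestibular tests. Section 12 (Data Storage) limits the stored data to vergence and vestibular results and does not list the MSQ.

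**The concern.** The safety question in SA1 concerns one test, while the safety measurement covers a whole session. The other tests include optokinetic stimulation, four smooth pursuit tests, several saccade tests and antisaccades. Dizziness or nausea on the MSQ could come from any of these, from wearing the goggles, or from symptoms present on arrival. Safety is half of what SA1 sets out to determine. Followed as written, the plan supports a statement about the full battery but not, once anyone reports a symptom, about vergence testing.

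A second, weaker issue is that the plan does not say where vergence falls in the session. If it comes late, the vergence score may carry fatigue from the tests before it. That would affect the control values in SA2, and the group comparison in SA3 if the two groups tire differently.

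**Working it through.** The plan gives no figure for symptom rates or fatigue, so there is no stated number to reproduce. The check is a count, a comparison of the sections, and some labelled illustrations.

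**1. Count of tests.** The Section 11 table has 17 rows: Vergence Pursuit and 17 − 1 = 16 others. This takes the Vergence Pursuit row to be the ternary-sequence vergence test, which the plan does not say. If they are separate, the other tests number 17. If the 15 minutes in Section 9 cover all 17 rows, each takes about 15 × 60 / 17 = 53 seconds.

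**2. Attribution under each possible order.**
- Vergence first: the MSQ still follows 16 further tests.
- Vergence last: the MSQ follows vergence directly, but 16 tests came before it and there is no earlier form to subtract.
- Vergence in the middle: both problems apply.

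No order lets a single end-of-session form isolate vergence. The SCAT-5 has the same timing, so it does not help.

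**3. What a single form can show for the 30 normal subjects.**
- Nobody positive: the exact one-sided 95% upper bound is 1 − 0.05^(1/30) = 9.5% (two-sided: 1 − 0.025^(1/30) = 11.6%). Because the battery includes vergence, this bound also covers vergence, provided that a short-lived symptom from early in the session is still reported at the end.
- k of 30 positive: the number due to vergence lies anywhere from 0 to k. An upper limit remains, but there is no estimate.

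**4. How far battery and vergence rates might differ (assumption, not from the documents).** Suppose that each of the 17 tests provokes a symptom independently and at the same rate p. The share positive at the end is 1 − (1 − p)^17.
- p = 1%: 1 − 0.99^17 = 15.7%, against 1% for vergence alone.
- p = 5%: 1 − 0.95^17 = 58.2%, against 5% for vergence alone.

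Equal rates are unlikely across, say, pupil reflex and optokinetic stimulation. If symptoms cluster in susceptible people, the battery figures would be lower.

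**5. Sensitivity of SA3 to differential fatigue (assumption, not from the documents).** Suppose that there is no true group difference, but fatigue shifts the mTBI mean by d standard deviations more than the control mean. With 30 per group and a two-sided 5% z-test, SE = √(2/30) = 0.258 and the rejection probability is 1 − Φ(1.96 − d/0.258) + Φ(−1.96 − d/0.258).

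| d | False-positive rate |
|---|---|
| 0 | 5.0% |
| 0.1 | 6.7% |
| 0.2 | 12.1% |
| 0.3 | 21.3% |
| 0.5 | 49.1% |

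Nothing in the documents says which row applies, or that d differs from zero.

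**The case against.** The strongest reply is that Section 4 ties the questionnaire to use of the goggles, and for that question an end-of-session form is adequate. This stands in part. It narrows the gap, but SA1 still names vergence testing, so the two sections ask different questions and need to be reconciled.

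It can also be said that the data are not useless: few or no symptoms after the whole battery would speak for vergence as well. That is right. The difficulty arises only when symptoms are reported.

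A reader might infer that the tests run in no fixed order, or in whatever order the operator picks. The documents do not support this. They are silent on order; the goggles are programmed in advance and Vergence Pursuit is listed first, so the order may already be fixed.

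A reader might also infer that fatigue will produce a false vergence deficit in mTBI. That needs vergence to be run late, material fatigue within a short session, and more of it in mTBI patients than in controls. None of these is shown. If vergence runs first, nothing carries over from the other tests. If the order is common to everyone, a shift shared by both groups largely cancels in SA3. One narrower point survives: the two groups are tested in separate phases, so an unwritten order that changed between phases would be confounded with group.

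**Conclusion.** The attribution gap is real and does not depend on test order. One form after vergence and 16 other tests can put an upper limit on vergence symptoms, and a clean form would support vergence safety. A positive form cannot be interpreted for SA1, because anywhere from none to all of the positives could be due to vergence. The 15.7% and 58.2% figures only illustrate how far the battery and vergence rates could diverge under equal, independent rates; they are not estimates for this trial.

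On order, the supportable statement is that it is not given. Carry-over into the vergence score arises only if vergence is not run first, biases SA3 only if it differs between groups, and cannot be sized from the documents. This is an inexpensive improvement to the design and does not invalidate the study.

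**What to change.** In Section 11:
- State that the ternary-sequence vergence test is run first for all 60 participants, both mTBI and normal, and say whether it is the Vergence Pursuit row of the table.
- Give the MSQ to both groups three times: before the session, immediately after vergence, and at the end.
- Base the SA1 safety statement on the change from the pre-session form to the form straight after vergence. The pre-session form is needed because symptoms already present would otherwise be counted against vergence.
- Report the end-of-session form as the safety of the whole goggle battery, in line with Section 4.

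In Section 12, add the MSQ to the stored data.

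The cost is protocol wording, a confirmed order in the goggle programme, and a few extra minutes per session for repeat passes of an existing questionnaire.

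If no extra form is wanted, the minimum is to restate the safety part of SA1 as safety of the full goggle battery, so that Sections 3 and 4 agree. That changes wording only, but gives up the vergence-specific question.
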